Tertiary aim: To investigate the association between objectively measured daily number of steps and patient-reported hip outcomes one year after initiation of treatment.

STUDY METHODS

Trial design

This study is a secondary analysis of data from the PreserveHip trial, a multicentre randomised controlled trial conducted at Aarhus University Hospital and Odense University Hospital in Denmark and at Oslo University Hospital in Norway. The PreserveHip trial was designed as a parallel-group superiority trial with a 1:1 allocation ratio. Participants were randomly assigned to either PAO followed by usual care and eight months of PRT or 12 months of PRT alone. The present secondary analysis focuses on objectively measured physical activity outcomes assessed one year after initiation of treatment. Analyses comparing the two intervention groups preserve the original randomisation. Comparisons with healthy subjects are observational and non-randomised. We prespecified and registered the PreserveHip

trial at ClinicalTrials.gov (NCT03941171), and we have previously published the trial protocol (15) and the blinded interpretation of the primary results (16). This statistical analysis plan (SAP) is reported in line with the ‘Guidelines for the Content of Statistical Analysis Plans in Clinical Trials’ (17), while the reporting of this secondary analysis will follow the “Consolidated Standards of Reporting Trials” (CONSORT) statement (18).

Randomization and blinding

After completion of baseline assessments, participants were randomised in a 1:1 ratio to either PAO followed by PRT or PRT alone. Randomisation was performed using a computer-generated allocation sequence implemented in REDCap (19, 20), with permuted blocks of variable size (4, 6, and 8). Allocation concealment was ensured through an external randomisation service provided by the Clinical Trial Unit, Department of Clinical Medicine, Aarhus University, Denmark. Due to the nature of the interventions, participants were not blinded to treatment allocation, whereas outcome assessors performing follow-up assessments were blinded.

Sample size and power considerations

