The primary analysis will be conducted in a modified intention-to-treat (mITT) population, defined as all randomised participants with valid baseline physical activity measurements. Valid physical activity measurements are defined as at least three valid days with a minimum of 10 hours of accelerometer wear time per day. This criterion is required for inclusion in the statistical analyses and for imputation of the one-year outcome. Randomised participants who do not meet this criterion will be excluded from the analyses. Activity measure from participants included in the mITT population will be analysed according to their originally assigned randomization group, irrespective of treatment adherence or treatment crossover. This population represents the treatment policy estimand and will be used for all analyses comparing participants randomised to PAO followed by PRT with participants randomised to PRT alone.

A sensitivity analysis following the same approach as the primary analysis will be performed based on the complete-case population. The complete-case population is defined as all randomised participants with both valid baseline and follow-up physical activity measurements.

Healthy subjects with valid physical activity measurements meeting the same accelerometer wear-time criteria will be included in a separate observational analysis population. Comparisons involving healthy subjects are non-randomised and exploratory.

TRIAL POPULATION

Eligibility

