The primary outcome is the objectively measured daily number of steps at one year after initiation of treatment, assessed using tri-axial accelerometry (AX3, Axivity Ltd., Newcastle, UK) with data post-processed using a custom-designed algorithm implemented in MATLAB (22, 23). The primary endpoint is the between-group difference in the estimated mean daily number of steps at one year between participants randomised to PAO followed by PRT and participants randomised to PRT alone. Baseline number of steps and the site of inclusion will be included as covariates in the statistical model. All physical activity-related outcomes are presented in Table 2. Additionally, the six dimensions of HAGOS will be used to assess patient-reported outcomes (21).

Analysis methods

Primary and secondary physical activity outcomes will be analysed using analysis of covariance (ANCOVA) models. For comparisons between randomised treatment groups, the outcome measured at one year will be modelled with randomization group as the main factor. The corresponding baseline value of the outcome and site of inclusion will be included as covariates to reduce random variation. The primary estimand is the between-group difference at one year, and results will be reported as adjusted mean differences with corresponding two-sided 95% confidence intervals. A sensitivity analysis following the same approach as the primary analysis will be performed based on the complete-case population.

Comparisons involving healthy subjects will be analysed using multiple linear regression with the outcome being activity measured at one year for the two intervention groups and activity measured at baseline for the healthy subjects. The groups will be the main factor and the analysis will be adjusted for age and sex. These comparisons are observational and exploratory.

Associations between objectively measured physical activity outcomes and HAGOS scores will also be analysed using multiple linear regression models, adjusted for age and sex. To assess whether the association between physical activity and HAGOS differs between randomisation groups, an interaction term between physical activity and randomisation group will be included in the model.

Missing data

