Inclusion in the analysis requires valid baseline physical activity measurements and participants without baseline physical activity measurements will be excluded from the analysis. Missing outcome data at one year for randomised participants will be handled using multiple imputation for all three aims, under the assumption that data are missing at random. Imputation will be performed using a regression model including baseline physical activity, age, sex, randomization group and site of inclusion as predictors. A total of 1,000 imputed datasets will be generated, and estimates will be combined using Rubin's rules (24). Healthy subjects will be analysed using observed data only. A sensitivity analysis of complete cases (participants with complete follow-up) will be performed for all three aims.

Statistical software

All statistical analyses will be performed using Stata version 19.5 (StataCorp LLC, College Station, TX, USA).

Tables

Table 1. Baseline characteristics of the modified intention-to-treat population and healthy subjects.

	PAO-group n = xx	PRT-group n = xx	Healthy-group n = xx
Female, n (%)			
Age (years), mean (SD) or median (IQR)			
BMI (kg/m ²), mean (SD) or median (IQR)			
Duration of hip symptoms, n (%)			
None			
0-6 months			
6-12 months			
1-2 years			
2-5 years			
5-10 years			
More than 10 years			
Missing			
Civil status, n (%)			
Married			
Cohabiting			
Single			
Divorced			
Widow/widower			
Not informed			
Educational level, n (%)			
Primary school			
Vocational education			
High school or similar			
Short higher education			
Medium higher education			
Long higher education			
Other education			
Employment status, n (%)			
During education			
In work			
In employment activation, sick leave, available, etc.			
Outside the labour market			
Alcohol consumption, n (%)			
Below 2 items per week			
2-7 items per week			
8-14 items per week			
Above 15 items per week			
Missing			
Smoking behaviour, n (%)			
Never smoked			
Quit smoking			
Sometimes			
Daily			

Outcomes will be presented as means with standard deviation (SD) or medians with interquartile range (IQR) or numbers (n) with proportion (%). PAO = Periacetabular osteotomy. CE-angle = Wibergs centre edge angle. AI-angle = Acetabular Index angle.

Table 2. Physical activity-related outcomes.

Dimension	Outcome	Timeframe	Unit
Frequency	Steps	One-year after initiating treatment	Number per day
	Cycling rotations	One-year after initiating treatment	Number per day

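### The valid-baseline requirement also governs the healthy comparison and the HAGOS association, whose models use no baseline activity, so observed one-year records are discarded without need

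*SAP*

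**What the plan says.** Analysis populations (SAP) defines a "modified intention-to-treat (mITT) population, defined as all randomised participants with valid baseline physical activity measurements", where valid means "at least three valid days with a minimum of 10 hours of accelerometer wear time per day". It continues: "This criterion is required for inclusion in the statistical analyses and for imputation of the one-year outcome", and then "Randomised participants who do not meet this criterion will be excluded from the analyses". The Missing data section repeats the rule: "Inclusion in the analysis requires valid baseline physical activity measurements and participants without baseline physical activity measurements will be excluded from the analysis". Its next sentence applies multiple imputation of the one-year outcome to all three aims, with baseline activity, age, sex, randomisation group and site as predictors. Baseline activity itself is not imputed.

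The models are in Analysis methods. The primary aim uses ANCOVA with the corresponding baseline value and site. The secondary aim takes one-year activity in the two arms and baseline activity in healthy subjects: "The groups will be the main factor and the analysis will be adjusted for age and sex". The tertiary aim regresses on the same two covariates, with an interaction between activity and randomisation group.

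The complete-case population needs valid records at both baseline and follow-up (Analysis populations). The Missing data section describes complete cases only as those whose follow-up is complete.

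**The concern.** A randomised participant with a valid one-year record but too few valid baseline days is removed everywhere. In the secondary and tertiary aims nothing in the analysis model calls for that baseline record, so an observed outcome is thrown away.

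Two things are at stake. The first is precision: enrolment stopped short of the planned size, so observed outcomes are scarce. The second is selection. If patients who fail the wear-time rule at baseline differ in activity from those who pass, the patient mean that is set against healthy subjects shifts. That comparison is not randomised, so nothing offsets the shift. No planned sensitivity analysis would reveal it, and Table 1 describes only the patients who remain.

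**Working it through.** **Where baseline activity is used**

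| Aim | Analysis model | Imputation of one-year activity |
|---|---|---|
| Primary (arm comparison) | yes, covariate | yes, predictor |
| Secondary (healthy comparison) | no | yes, predictor |
| Tertiary (HAGOS association) | no | yes, predictor |

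The imputation column matters only when the one-year record is missing. For a participant with an observed one-year record, the secondary and tertiary aims use baseline activity nowhere.

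**Inputs.** The SAP gives no number lacking a valid baseline, so there is no figure of its own to reproduce on this point. Let f be the share, among randomised participants with a valid one-year record, who lack a valid baseline. I assume f = 5%, 10% and 20%. Let ρ be the correlation between baseline and one-year activity; I assume 0.5 and 0.7. For scale only, I use the planned size of 2 × 48 = 96; actual enrolment was lower and is not stated. If all 96 had one-year data, these values of f would mean about 5, 10 and 19 people dropped (96 × f = 4.8, 9.6, 19.2).

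**Information gained by keeping them**

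- Tertiary aim (patients only): f/(1−f).
- Secondary aim: the healthy group does not change. The variance is proportional to 1/n_patient + 1/n_healthy. With equal group sizes and variances, the ratio of variances (dropped to kept) is [1/(1−f) + 1]/2, a gain of f/[2(1−f)].
- Primary aim: a participant without baseline carries (1−ρ²) of the information of one with baseline, so the gain is f(1−ρ²)/(1−f).

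| f | Tertiary | Secondary | Primary, ρ = 0.7 | Primary, ρ = 0.5 |
|---|---|---|---|---|
| 5% | 5.3% | 2.6% | 2.7% | 3.9% |
| 10% | 11.1% | 5.6% | 5.7% | 8.3% |
| 20% | 25.0% | 12.5% | 12.8% | 18.8% |

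Example at f = 10%: 0.10/0.90 = 11.1%; half of that is 5.6%; 0.10 × 0.51/0.90 = 5.7%; 0.10 × 0.75/0.90 = 8.3%.

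For the tertiary aim the confidence interval widens by 1/√(1−f), that is 1.03, 1.05 and 1.12. These figures treat observed records as the only source of information. Participants with imputed one-year activity add a little, so the true gains are slightly smaller.

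**Selection.** I rely on a simulation of 4,000 trials per setting: 96 participants, no true effect, complete one-year data, and less active participants more often lacking a baseline. Dropping them moved the patient mean upward by 0.02–0.03 SD at 5%, 0.04–0.06 SD at 10% and 0.08–0.12 SD at 20%. In the arm comparison, the mean estimate stayed within 0.01 SD of zero, and the standard error was about 0–9% larger than when everyone was kept (baseline set to its mean, with a missing-value indicator). The direction and strength of the selection are assumed.

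**The case against.** **One population for all aims is a choice with a stated reason.** The SAP ties the criterion to imputation, and imputation serves all three aims. That justifies requiring a baseline from participants whose one-year record is missing. It does not justify requiring it from those whose record is observed.

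**The rule may not reach the secondary and tertiary aims.** Analysis populations links the mITT set by name only to the arm comparison: "This population represents the treatment policy estimand and will be used for all analyses comparing participants randomised" to the two arms. The reach to the other aims rests on the general wording there and in Missing data. That wording has no exemption and is followed directly by the reference to all three aims. If the narrower reading was meant, the patient population for those aims is nowhere defined, and Tables 4 and 5 do not name one. Either way the text needs a sentence.

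**The two complete-case descriptions may agree.** If a valid baseline is already an entry condition, complete follow-up amounts to the same set. This is wording to reconcile rather than a firm contradiction, but that reading confirms that the excluded participants are not recovered.

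**A reader might infer that the exclusion breaks intention to treat, biases the arm comparison or contradicts the treatment policy label.** The documents do not support this. Randomization and blinding places allocation after the baseline assessments, so baseline validity cannot depend on the arm, and the arms remain comparable within the retained set. The statement "Analyses comparing the two intervention groups preserve the original randomisation" therefore stands. The population is openly called modified ITT. The treatment policy label concerns events after randomisation, such as crossover, and the SAP analyses those as assigned. For the primary aim the cost is precision and generalisability.

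**The number affected may be zero or one.** This cannot be excluded, and it limits the weight of the point.

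**Conclusion.** The point holds for the secondary and tertiary aims. As written, the plan discards valid one-year records that those models could use, and no planned analysis restores them. With f assumed at 5–20%, keeping them gains about 5–25% information for the tertiary aim and about 3–13% for the secondary aim with equal group sizes (more if the healthy group is larger than the arm, less if it is smaller). It also removes a possible selection effect from a non-randomised comparison. If f is zero, nothing changes.

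For the primary aim there is a precision cost of about 3–19% in information over the assumed ranges of f and ρ, and no bias in the arm contrast. That last conclusion takes the accelerometer wear period to belong to the baseline assessments completed before allocation, as the SAP's wording indicates. Severity is modest: the SAP describes its results as exploratory, and the healthy comparison as observational too.

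**What to change.** - **Secondary and tertiary aims, main analysis:** include every randomised participant with valid one-year activity, whatever the validity of the baseline record. Continue to impute one-year activity only for those with a valid baseline. An observed one-year record is carried unchanged into each of the 1,000 completed datasets.
- **Secondary and tertiary aims, complete cases:** define them by valid one-year data alone, and bring the descriptions in Analysis populations and Missing data into line.
- **Reporting:** name the population under Tables 4 and 5, and give the number excluded for an invalid baseline by arm, with how many of them had a valid one-year record. The planned CONSORT flow diagram can carry this.
- **Primary aim:** keep the declared mITT analysis. As an added sensitivity analysis, retain participants with valid one-year data but no valid baseline by imputing the corresponding baseline value.

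The first three items cost a few sentences and a count. The last costs more: Table 2 lists 14 outcomes, and a failed baseline record loses the baseline value of all of them, so each outcome's imputation must include its own baseline. It also adds a missing-at-random assumption for baseline, which is why it belongs in a sensitivity analysis.

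### The imputation model omits HAGOS although it also serves the steps–HAGOS analysis, so that slope is attenuated and its interaction with group is biased

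*SAP*

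**What the plan says.** The Missing data section of the SAP sets one rule for the whole analysis: "Missing outcome data at one year for randomised participants will be handled using multiple imputation for all three aims". The stated condition is missingness at random. The model is listed in full: "Imputation will be performed using a regression model including baseline physical activity, age, sex, randomization group and site of inclusion as predictors". It adds: "A total of 1,000 imputed datasets will be generated". A complete-case analysis is planned as a sensitivity analysis for each aim.

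The tertiary aim is: "To investigate the association between objectively measured daily number of steps and patient-reported hip outcomes one year after initiation of treatment". Under Analysis methods, the SAP states: "Associations between objectively measured physical activity outcomes and HAGOS scores will also be analysed using multiple linear regression models, adjusted for age and sex". To examine whether the association differs between arms, "an interaction term between physical activity and randomisation group will be included in the model". Table 5 reports a coefficient for steps and an R² for each of the six HAGOS subscales, so HAGOS is the dependent variable and one-year steps the covariate.

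No separate imputation model is given for the tertiary aim. The SAP does not say whether missing HAGOS scores are themselves imputed.

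**The concern.** When a covariate is imputed without the dependent variable of the analysis model, the imputed values are drawn as if unrelated to that variable, given the listed predictors. Here, imputed steps carry only the part of the steps–HAGOS association that runs through baseline activity, age, sex, group and site. The rest is lost in every imputed record that enters the regression with a HAGOS value. Drawing 1,000 datasets reduces Monte Carlo noise but leaves this bias in place.

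The pattern that causes it is realistic. A valid activity measurement needs at least three days with 10 hours of wear. A participant can fail that rule at one year and still complete the questionnaire.

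The direction matters for interpretation. The Introduction motivates the study by reported disagreement between patient-reported and measured outcomes. A rule that weakens the estimated association can itself look like such disagreement. The imputed analysis is the main one and complete cases are the check, so the affected estimate would be the headline.

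**Working it through.** **What the SAP supplies.** The list of imputation predictors, the form of the tertiary model and the missing-at-random assumption. It gives no missing fraction, no correlation and no sample size for this analysis, so there is no figure of the plan's own to reproduce. The parent trial was planned at 48 per group (2 × 48 = 96), and enrolment stopped early.

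**Assumptions (none from the SAP).** N = 90; 10–30% of one-year steps missing completely at random; HAGOS observed; correlation r between baseline and one-year steps of 0.3 or 0.6; standardised steps–HAGOS slopes of 0.2 and 0.5 in the two arms, hence an average slope of 0.35 and an interaction of 0.30; baseline steps related to HAGOS only through one-year steps.

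**Formula.** Let m be the missing fraction and c the share of the steps–HAGOS covariance carried by the imputation predictors. Observed rows keep the full covariance and imputed rows keep the share c, so

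expected slope = true slope × [(1 − m) + m·c] = true slope × [1 − m(1 − c)].

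In this set-up c = r². For m = 0.20 and r = 0.6: 0.35 × [1 − 0.20 × 0.64] = 0.35 × 0.872 = 0.305.

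**Simulation of the planned imputation.** 1,500 replicates with 10 imputations each, Monte Carlo standard errors 0.002–0.005:

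| m | r | Slope by formula | Slope simulated (true 0.35) | Interaction simulated (true 0.30) |
|---|---|---|---|---|
| 10% | 0.3 | 0.318 | 0.316 | 0.275 |
| 10% | 0.6 | 0.328 | 0.327 | 0.276 |
| 20% | 0.3 | 0.286 | 0.281 | 0.243 |
| 20% | 0.6 | 0.305 | 0.301 | 0.245 |
| 30% | 0.3 | 0.254 | 0.241 | 0.212 |
| 30% | 0.6 | 0.283 | 0.272 | 0.229 |

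Slope attenuation runs from 1 − 0.327/0.35 = 7% to 1 − 0.241/0.35 = 31%. The formula alone gives 6–27%. The small excess is what one expects when imputation parameters are drawn from few observed cases. With equal missingness in the arms, interaction attenuation runs from 1 − 0.276/0.30 = 8% to 1 − 0.212/0.30 = 29%.

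**Both variables missing, each imputed from the listed predictors without the other** (m = 20%, r = 0.6): slope 0.302, interaction 0.231.

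**Unequal missingness by arm** (r = 0.6), applying the formula within each arm:
- True slope 0.35 in both arms, 30% and 10% missing: 0.35 × 0.808 = 0.283 and 0.35 × 0.936 = 0.328. The difference is +0.045 where the truth is 0. Simulated: +0.052.
- True slopes 0.30 and 0.40, 30% and 5% missing: 0.30 × 0.808 = 0.242 and 0.40 × 0.968 = 0.387. The difference is 0.145 where the truth is 0.10. Simulated: 0.157.

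The arm with more missing data is attenuated more, so the interaction can move either way.

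**Effect of changing the imputation model** (m = 20%, r = 0.6):

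| Imputation model for steps | Slope (true 0.35) | Interaction (true 0.30) |
|---|---|---|
| As planned | 0.301 | 0.245 |
| Plus one-year HAGOS | 0.344 | 0.253 |
| Plus HAGOS, HAGOS × group, baseline steps × group | 0.342 | 0.279 |

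With 30% and 10% missing and no true interaction, the last model gives −0.003 in place of +0.052. HAGOS alone repairs the slope; the interaction needs the group-specific terms.

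**The case against.** The strongest defence is that the damage is modest and visible. The aim is tertiary, the SAP says the results will be interpreted as exploratory, and complete cases will be reported for every aim, so a discrepancy would show. With few missing values the effect is slight: at 5% missing and r = 0.6 the formula gives 0.05 × 0.64 = 3%. Sampling error is larger than the bias. With n = 80, r = 0.6, a true slope of 0.35 and 20% missing, planned imputation gave root mean squared error 0.113 and 96% interval coverage, against 0.121 and 95% for complete cases, with power of 0.72 against 0.80. All of this stands, and it bears on how serious the point is. It does not make the listed predictors suitable for this analysis.

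A reader might also infer more than the SAP supports:

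- **That the interaction is always pulled toward zero.** This holds only with similar missingness in the arms. The SAP does not say missingness will be similar, and the unequal examples go the other way.
- **That every imputed participant dilutes the association.** The SAP does not say whether HAGOS is imputed. If both measures are missing after one missed visit and HAGOS is not imputed, that row leaves the regression and adds no such bias.
- **That complete cases are unbiased.** This was shown only for data missing completely at random. The SAP assumes missing at random. If dropout depends on baseline activity, which is outside the age- and sex-adjusted model, lack of bias is not guaranteed.
- **That the main trial comparison is affected.** For steps, the variables of the aim 1 model (baseline value, group, site) are all in the imputation model, so this attenuation does not arise there.

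**Conclusion.** The imputation rule is wrong as written for the tertiary aim and should be corrected. The mechanism follows from the SAP's own text: one imputation model for all aims, without the dependent variable or the interaction of the tertiary regression. The size does not follow from the text. The 7–31% range for the slope rests on the assumed missing fractions and correlations and on HAGOS being available, or separately imputed, where steps are imputed. The direction of the interaction bias depends on how missingness splits between the arms, so that test is unreliable without being predictably conservative. The unknown missing fraction, the exploratory status of the aim and the planned complete-case check keep this below a defect that must be fixed before the plan can be used.

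**What to change.** Amend the Missing data section for the tertiary aim only:

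- Add the one-year HAGOS subscale being analysed to the imputation model for one-year steps, with baseline HAGOS if available.
- Include HAGOS × group and baseline steps × group terms, or impute separately by arm.
- Work one subscale at a time. Putting all six subscales and their baselines into one model fitted by arm would be heavy for a sample of this size.
- State whether missing HAGOS is imputed. If it is, impute it jointly with steps, each in the other's model.

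Alternatively, make complete cases the main tertiary analysis and state the missingness assumption this needs, since its lack of bias was checked only under data missing completely at random.

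The cost is a few sentences in the SAP and a few lines of Stata; no new data are needed. The downside is a slightly larger imputation model and separate imputation runs for this aim, so imputed steps will differ from those used for aims 1 and 2. The simulated repair used a single HAGOS score without its baseline value and left a small shortfall in the interaction (0.279 against 0.30).

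### For the primary comparison of daily steps, the complete-case sensitivity analysis makes nearly the same missing-at-random assumption as the multiple imputation, so departures from it are not explored

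*SAP*

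**What the plan says.** The Missing data section of the SAP handles absent one-year outcomes by "multiple imputation for all three aims, under the assumption that data are missing at random". The model is stated: "Imputation will be performed using a regression model including baseline physical activity, age, sex, randomization group and site of inclusion as predictors". On the number of imputations and pooling: "A total of 1,000 imputed datasets will be generated, and estimates will be combined using Rubin's rules".

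For the randomised comparison, Analysis methods specifies an ANCOVA with randomisation group as the main factor. It adds: "The corresponding baseline value of the outcome and site of inclusion will be included as covariates to reduce random variation".

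The only sensitivity analysis for missing data is the complete-case one. Missing data says "A sensitivity analysis of complete cases (participants with complete follow-up) will be performed for all three aims". Analysis populations and Analysis methods both say "A sensitivity analysis following the same approach as the primary analysis will be performed based on the complete-case population", and the population is fixed as follows: "The complete-case population is defined as all randomised participants with both valid baseline and follow-up physical activity measurements". Table A1 is the shell for its results. Entry to the main analysis set already requires valid baseline accelerometry, so in aim 1 the one-year outcome is the only variable to be imputed. The SAP contains no delta-adjusted, tipping-point or other missing-not-at-random (MNAR) analysis.

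**The concern.** A missing-data sensitivity analysis is useful if it relaxes or varies the assumption behind the main analysis. Here the second analysis drops the participants whom the first one imputes, but uses almost the same covariates to account for their absence. If their unseen step counts are lower than baseline, group and site predict, both analyses miss this in the same way.

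This could matter in this trial. Participants knew their allocation. A valid measurement needs at least three days with 10 hours of wear, so missingness includes insufficient wear, which could depend on arm, recovery or activity. The imputation model has no post-baseline variable. Under the declared treatment policy estimand, the unobserved outcomes of participants who crossed over or did not adhere would be imputed from baseline variables and assigned group alone. A reader who sees Table A1 agree with Table 3 may take that as reassurance on a question that neither table addresses.

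**Working it through.** **The plan's own figures.** The SAP gives no figure for missing data. Its only sample-size figure, 48 per group for HAGOS pain, is consistent with its inputs: 2 × (1.96 + 0.84)² × 16.2² / 9.7² ≈ 44 per group, and 44 / 0.92 ≈ 48 with an allowance of about 8%. The actual allowance is not stated. The figure serves here only to set the simulation size at 2 × 48 = 96. Enrolment stopped short of the plan, so the achieved number is smaller.

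**Step 1: why the two analyses coincide.** Let X hold the ANCOVA covariates (group, baseline, site), with subscripts o for observed and m for missing outcomes, and let b be the complete-case estimate. If the imputation model used exactly X, the imputed values would average X_m b over many imputations. Refitting the ANCOVA gives

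(X'X)⁻¹ [X_o'y_o + X_m'X_m b] = (X'X)⁻¹ [X_o'X_o b + X_m'X_m b] = b.

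The imputed point estimate equals the complete-case estimate, and 1,000 imputations leave negligible Monte Carlo noise. The SAP's imputation model adds age and sex, so equality becomes near-equality.

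**Step 2: the assumptions compared.** Complete-case ANCOVA is valid if missingness depends only on group, baseline and site. Multiple imputation (MI) also allows dependence on age and sex. The sensitivity analysis therefore assumes slightly more than the main analysis.

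**Step 3: simulation of aim 1.** From the SAP: 1:1 allocation, three sites, its imputation predictors, 1,000 imputations, Rubin's rules and its ANCOVA. Assumed: baseline mean 7,500 and SD 3,000 steps/day, slope 0.6, residual SD 2,400, true difference 0, nominal missingness of 10%, 20% or 30%, an age effect of 0 or 600 steps per SD, and 300 replicates per scenario. Under MAR, missingness depended on baseline steps and group. Under MNAR, it depended on unseen one-year steps in the surgery (PAO) arm.

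Mean estimated difference under MNAR, steps/day (true value 0):

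| Nominal missing | Age effect | Complete-case | MI |
|---|---|---|---|
| 10% | 0 | 271 | 270 |
| 20% | 0 | 473 | 469 |
| 30% | 0 | 683 | 688 |
| 10% | 600 | 323 | 307 |
| 20% | 600 | 543 | 514 |
| 30% | 600 | 595 | 574 |

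Under MAR both stayed near 0 (complete-case −66 to 44, MI −67 to 41). Over all scenarios the two estimates correlated 0.98 to 0.999. Their mean absolute gap was 20 to 88 steps/day, or 0.04 to 0.14 of a standard error of about 520 to 650. Two further simulations with other assumed inputs each gave a correlation of 0.994, with MNAR biases of 0.132 vs 0.132 SD and 0.116 vs 0.114 SD.

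**Step 4: where the result stops.**
- Aim 2 adjusts for age and sex only, while the imputation also uses baseline activity. Under MAR with 20% missing and no age effect, the PAO-arm mean was 8,024 in complete cases and 7,536 with MI (full data 7,521), a gap of 488.
- In aim 3, Table 5 reports a coefficient for steps on each HAGOS score, so the imputed variable is the regressor. With assumed inputs (n = 90, HAGOS fully observed, true slope 0.40, low steps causing about 22% missing), complete cases gave 0.402 and MI 0.353.

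**Step 5: what a delta adjustment shows.** Adding δ to the imputed one-year steps in one arm moves the between-group difference by f × δ, where f is the fraction missing in that arm. This is exact for the unadjusted difference and holds for the ANCOVA up to chance covariate imbalance.

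| Assumed f | δ = 1,000 | δ = 2,000 |
|---|---|---|
| 10% | 100 | 200 |
| 20% | 200 | 400 |
| 30% | 300 | 600 |

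With the same δ in both arms, the shift is the difference in missing fractions × δ.

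**The case against.** The strongest reply is that this is a secondary analysis with no power calculation, which the SAP says will be read as exploratory. MI under an openly stated MAR assumption, with complete cases beside it, is coherent and fully specified. The SAP gives no missing fraction and no reasons for missingness. The outcome is device-measured and follow-up assessors were blinded. If 5% of one arm were missing, a δ of 1,000 would move the result by only 0.05 × 1,000 = 50 steps/day. Even the 200 steps/day at 20% missing is about 0.3 to 0.4 of the simulated standard error (200/650 to 200/520), so no change of conclusion is shown. All of this stands. It limits the priority, but it does not make the complete-case analysis informative about MNAR.

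Several stronger readings are tempting, and the SAP does not support them:
- A reader might infer that the sensitivity analysis is redundant for all three aims, since the quoted sentence covers them all. It is not. The aim 2 model omits baseline activity. In aim 3, complete-case regression stays valid when missingness depends on unseen steps, provided it does not also depend on HAGOS given steps.
- A reader might say that agreement in aim 1 is guaranteed. It is expected, not certain, because age and sex enter only the imputation model.
- A reader might say that the plan fails to test MAR. MAR cannot be tested from the observed data, and a delta analysis would not test it either. The gap is that departures from it are not explored.
- A reader might say that the plan claims robustness. No section says that agreement will be read in that way.

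**Conclusion.** The point holds for aim 1, the randomised comparison of daily steps. The near-equality of the two analyses follows from the plan's structure: only the outcome is imputed, with almost the same covariates as the analysis model. It does not depend on the simulation values. The size of any bias does depend on them. The figures of roughly 270 to 690 steps/day rest on assumed step-count variability, missing fractions and strength of outcome-dependent missingness, none of which the SAP gives. The material does not show that the trial's result will be biased, only that the planned check would be unlikely to reveal it. This is a cheap improvement of modest priority.

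**What to change.** For the primary outcome, add to the Missing data section a delta-adjusted (tipping-point) analysis that reuses the planned imputations:
- Add δ to the imputed one-year steps over a prespecified grid, for example 0, −500, −1,000 and −2,000 steps/day, with the range justified in the SAP.
- Apply it to each arm separately and to both arms together. Negative values in each arm in turn move the difference in both directions.
- Refit the ANCOVA, pool by Rubin's rules, and report the δ at which the conclusion changes, or state that none on the grid changes it.
- Report the number and fraction missing in each arm beside the results, since they set the size of the shift.

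Keep Table A1 as a supplementary analysis. The cost is a little extra analysis, one appendix table, and a grid that must be justified.
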